Principal Investigator: [name].

Co-Investigators: (including VA and WOC staff): While all research staff are trained to obtain informed consent, those identified with an asterisk (*) will obtain informed consent for this study. The PI and the listed research team will have access to PHI.

Co-Investigators: [name]., Ph.D., [name]., [name]., [name]. [name], [name], [name] [name]

Authorized Prescribers: [name]., [name]., Ph.D., [name]., [name] [name]

Nursing Staff: [name], R.N.,

Psychologists: J. [name].

Research Staff: [name], [name], [name], [name], [name]

Title of Project: Buprenorphine/Naloxone Treatment for Prescription Opioid Dependence

Purpose: Although buprenorphine/naloxone (BUP/NLX) treatment is effective for the treatment of prescription opioid dependence, previous studies have not determined the optimum dose of BUP/NLX for this patient population. The goal of this study is to determine if there are differences in clinical efficacy of BUP/NLX tablet in low dose range (less than or equal to 8/2mg) vs. high dose range (greater than or equal to 16, range 16-24mg). The main outcomes of interest will be treatment retention, use of opioids, and the use of other drugs of abuse.

Introduction:

Prescription opioid abuse, including oxycodone, hydrocodone, hydromorphone, morphine, codeine, propoxyphene, and methadone, has emerged as a major public health problem particularly in the United States, which represents about 5 percent of the world's population but consumes 80 percent of the global opioid supply and 99 percent of the global hydrocodone supply (Sehgal et al., 2012). Prescriptions for opioid medications have increased dramatically with 174 million prescriptions dispensed from retail pharmacies nationally in 2000, increasing to 257 million prescriptions by 2009 (Food and Drug Administration (FDA), 2010). According to data from the Centers for Disease Control and Prevention ((CDC), deaths due to prescription opioids went from 1.3 per 100,000 in 1999 to 5.0 per 100,000 in 2008, resulting in 14,800 prescription painkiller deaths in 2008 (Centers for Disease Control and Prevention, 2012).

Furthermore, deaths from prescription opioids have dramatically increased over the past 10 years and are now the second leading cause of accidental death in the US (Okie, 2010).

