This will be a randomized, open-label clinical trial. Veteran opioid dependent men and women will be randomized to one of two treatment groups: low dose range of BUP/NLX (Less than or equal to 8mg) vs. high dose range of BUP/NLX (Greater than or equal to 16mg). During induction into buprenorphine, all participants will be started at a dose of 2mg, and this dose will be increased as needed for stabilization of opioid withdrawal symptoms, up to 8mg for the low dose group, and up to at least 16mg for the high dose group, within about 7 day period. If a participant is randomized to the low dose group but is experiencing withdrawal symptoms that cannot be stabilized the participant will be discharged from the study. Participants will be clinically managed and will get monthly assessments. Participants will be seen on a daily basis (excluding weekends) for the initial 7 day induction. Once subjects are on maintenance dose of BUP/NLX (goal is within 5 days), they will be seen weekly by study RN for medical management, symptom evaluation, and medication refill. Participants will also complete study questionnaires at this time. At the end of the 12-week study, participants will either be referred to a buprenorphine clinic if they wish to continue this medication, or if they wish to be drug free, will undergo detoxification from BUP/NLX for up to a 4-week period. Follow-up visits, scheduled at 1, 3, and 6 months after study completion, will evaluate the durability of treatment effects on drug use and psychosocial outcomes.

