mg/day. In this study, a combination tablet will be used, since it is less likely to be diverted than the buprenorphine only formulation. Consistent with the clinical guidelines, before BUP/NLX is administered, participants will be instructed not to use any prescription opioids for 24 hours and be prepared to stay in the clinic for at least 2 hours following the first dose of BUP/NLX. On the induction day, participants in the low dose group will start with 2/5 mg but may receive a maximum of 4/1 mg of BUP/NLX, and will be assessed by a physician in the clinic for up to 2 hours for signs and symptoms of opioid withdrawal. Participants in the high dose group will also start with a 2/5 mg but may receive additional doses of BUP/NLX on the induction day if initial BUP/NLX doses do not suppress opioid withdrawal adequately. Between days 2 and 5, the dose may be gradually increased to the target dose based on the response of the patient: (1) low dose subjects will be held as low as tolerated with a maximum of 8 mg and (2) high dose subjects will be increased to at least 16 mg. At the end of the trial, subjects will receive *up to* a four-week buprenorphine taper depending on individual needs. Buprenorphine/Naloxone is a Schedule III drug that, in community settings, is often prescribed for up to a one month's supply at a time. Patients are generally seen on a weekly or monthly basis like those treated with other psychiatric medications. Buprenorphine/Naloxone will be delivered by the research pharmacy on the day of the participant's weekly appointment, and will be returned to the research pharmacy should the subject fail to present for the appointment. Buprenorphine/Naloxone treatment is generally well tolerated. Its side effects, such as abdominal pain, constipation, nausea, vomiting, headache, sweating, sedation, and allergic reaction are similar to other opioids. Increases in liver enzymes and hepatitis are rarely reported. Participants will be educated to keep their medication in a safe place to prevent unintentional exposure to others, especially children.

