- C. SAFTEE: The SAFTEE is a technique for the systematic assessment of side effects in clinical trials. The SAFTEE will be reviewed by the study nurse and specific symptoms, as well as severity, will be recorded. The SAFTEE will be administered weekly.

Data Analysis Methods:

A. Sample Size and Power Analysis:

For this pilot study, we will recruit a total of 200 subjects, 100 subjects in each treatment arm. No previous studies have examined the influence of BUP/NLX dose on treatment outcomes in prescription-opioid dependent individuals. Our sample of 200 will require an effect size of .25 to detect differences between the two treatment groups for the number of opioid positive urines during the treatment period.

B. Statistical analysis:

The principal analyses will be done on the modified intention to treat sample, that is, subjects receiving at least one dose of BUP/NLX. First, we will determine the success of the randomization by comparing the two treatment groups on socio-demographic and baseline clinical characteristics using chi-square for categorical variables and ANOVA for continuous variables. Second, survival analysis will be used to determine differences between experimental groups in treatment retention. Third, random regression analyses (HLM), (Hedeker and Gibbons 1996) will be conducted to examine if the change in opioid use behavior over time varies as a function of the treatment factors.

Risks and Benefits:

Potential risks

1. Buprenorphine: Buprenorphine, formulated as a sublingual tablet, is available alone or in combination tablet containing buprenorphine and naloxone in a ratio of 4:1. The doses of buprenorphine/naloxone used here are within the recommended guidelines of the manufacturer (4-24 mg/day). In this study, combination tablet will be used, since it is less likely to be diverted than the buprenorphine alone formulation. Common side effects of buprenorphine/naloxone include abdominal pain, constipation, nausea, vomiting, headache sweating, sedation, and allergic reaction. Uncommon but more serious adverse effects of buprenorphine/naloxone include hepatic abnormalities, orthostatic hypotension and respiratory depression.
2. Buprenorphine/Naloxone detoxification: Detoxification from buprenorphine/naloxone can produce signs and symptoms of opiate withdrawal, including nasal congestion, abdominal symptoms, anxiety, myalgia, insomnia, sweating, and diarrhea.

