3. Blood Drawing: Subjects will have approximately 80 cc of blood drawn as a result of their participation in the study. Blood drawing can cause some pain and may result in bruising and rarely, infection.
4. Nonspecific Risks: Other risks from the counseling, rating scales and urine collections are not beyond usual clinical procedures in a substance abuse treatment program. Confidentiality of these results are specifically protected by Federal laws, and all records will be identified by code number only, with the master file kept under lock by the Principal Investigator or Data Manager.

Risk/Benefit Ratio: This study may help to develop more effective treatment approaches for prescription opioid dependence.

Protection of subjects

- a. Our inclusion and exclusion criteria will be applied by experienced professionals who will be carefully trained and monitored in order to accept only appropriate subjects into the study. Thus, effective screening will exclude subjects who would be placed at an unacceptable risk. This is determined by the medical and psychiatric history, drug use history, the physical

examination, and the laboratory studies done prior to beginning this research protocol (although as stated previously, should a potential participant present already in withdrawal, it will be the decision of the study MD whether or not to randomize the patient prior to laboratory results being available.)

- b. Confidentiality will be protected by having records identified by code number only with the master list including names kept in locked file cabinets in Bldg. 36 . Confidentiality in this study is of the utmost importance to us. All information obtained will be stored in coded form. The paper files will be kept in locked file cabinets in Bldg. 36 and the electronic records will be kept within the VA intranet (M-drive).

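### Limiting the principal analyses to dosed participants deletes any retention failure before the first dose, which biases the comparison if such losses differ between arms

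*Combined protocol and SAP*

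**What the plan says.** Data Analysis Methods, B. Statistical analysis, defines the set for the principal analyses as a modified intention-to-treat sample, namely "subjects receiving at least one dose of BUP/NLX". The baseline comparison, the retention analysis and the random regression of opioid use all follow under that sentence. For retention the plan is that "survival analysis will be used to determine differences between experimental groups in treatment retention".

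The Purpose section puts retention first among the outcomes: "The main outcomes of interest will be treatment retention, use of opioids, and the use of other drugs of abuse". The Research Plan gives the design: "This will be a randomized, open-label clinical trial".

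Both the Research Plan and the Buprenorphine section give the two arms the same starting dose. The arms differ in what may follow on the induction day: the Buprenorphine section sets a maximum for the low-dose arm and allows further doses in the high-dose arm.

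The document contains no all-randomised analysis, no sensitivity analysis and no expected number of never-dosed participants. It does not say when randomisation takes place, or when the participant learns the arm, relative to the first dose.

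**The concern.** Membership of the principal set is decided after randomisation, by whether a first dose was taken. In an open-label trial the decision to start can depend on the assigned arm. A participant who leaves between randomisation and first dose has not been retained, yet the rule removes that person from the retention analysis instead of counting the failure.

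If equal numbers of similar people are lost from each arm, little harm is done. If the losses differ in number or prognosis, the groups compared are no longer those formed by randomisation, and the arm that more people decline looks better than it should. The check on whether randomisation succeeded has the same weakness, because it is planned on the dosed set.

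**Working it through.** The plan gives no figure for never-dosed participants, so there is none to reproduce. The only inputs from the document are 100 participants per arm and the at-least-one-dose rule. The retention rates and never-dosed shares below are assumptions, chosen to show a range.

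**Illustration 1: equal retention among those dosed.** Let r be retention among dosed participants and q the never-dosed share of an arm. Never-dosed participants count as not retained, so

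all-randomised retention = r × (1 − q).

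Take r = 0.60 in both arms. The modified analysis then shows 0.60 − 0.60 = 0 in every row.

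| q low | q high | Low arm, all randomised | High arm, all randomised | Difference (points) |
|---|---|---|---|---|
| 0% | 0% | 0.60 × 1.00 = 0.600 | 0.60 × 1.00 = 0.600 | 0 |
| 5% | 2% | 0.60 × 0.95 = 0.570 | 0.60 × 0.98 = 0.588 | 1.8 |
| 10% | 2% | 0.60 × 0.90 = 0.540 | 0.60 × 0.98 = 0.588 | 4.8 |
| 15% | 5% | 0.60 × 0.85 = 0.510 | 0.60 × 0.95 = 0.570 | 6.0 |

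The zero in the modified analysis describes retention among people who started. It does not describe what happened to the groups as randomised.

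**Illustration 2: equal retention among all randomised, with never-dosed participants in the low arm only.** This is a deliberately one-sided case. Here modified retention = all-randomised retention / (1 − q). With 50% in both arms:

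- q = 2%: 0.50/0.98 = 0.510, a spurious 1.0 points favouring the low arm
- q = 5%: 0.50/0.95 = 0.526, 2.6 points
- q = 10%: 0.50/0.90 = 0.556, 5.6 points
- q = 15%: 0.50/0.85 = 0.588, 8.8 points

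Under an unpooled normal approximation with 98, 95, 90 or 85 dosed in the low arm against 100 in the high arm, a nominal two-sided 5% test rejects in about 5.2%, 6.6%, 12.0% and 22.6% of trials. For q = 10%, the standard error is √(0.556 × 0.444/90 + 0.25/100) = 0.072, and the shift is 0.056/0.072 = 0.77 standard errors. If q is the same in both arms, the spurious difference is 0.

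**The case against.** The strongest reply is that few people may be lost before the first dose. The rule turns on one dose, which is the same in both arms. The arm-related loss that the Research Plan does describe, discharge of low-dose participants whose withdrawal cannot be stabilised, follows dosing, so those people stay in the set. The rates above are all assumed, and illustration 1 always puts more loss in the low arm. With 60% retention and 100 per arm, the standard error of a difference is √(2 × 0.24/100) = 6.9 points, larger than the biggest figure in that table.

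Most of this stands as a limit on likely size. It does not justify the exclusion. A systematic shift smaller than one standard error still raises the error rate, as illustration 2 shows for its one-sided case. If undosed losses are rare, analysing everyone costs almost nothing.

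Three stronger readings are tempting, and the document supports none of them:

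- The Buprenorphine section says that before BUP/NLX "participants will be instructed not to use any prescription opioids for 24 hours". A reader might infer a day in which people can refuse after learning their arm. The period is not placed after randomisation. The Subjects section requires withdrawal signs for eligibility, which suggests, without proving, that some abstinence comes earlier.
- Protection of subjects, item a, lets the study physician decide "whether or not to randomize the patient prior to laboratory results being available". A reader might see a gap before dosing. The provision concerns people already in withdrawal, and Entry into Treatment says that such people may need to start drug before results return, which points to a short gap.
- The differing induction-day rules might be taken to prove that participants know their arm before the first dose. They show that assignment exists by that day. Because the first dose is common, earlier knowledge remains an inference from the open-label design.

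**Conclusion.** The point holds as a conditional one. As written, the rule removes every participant lost between randomisation and first dose from all the principal analyses, in an open-label trial with retention as a main outcome, and no other analysis would reveal the loss. The retention comparison is biased if those losses differ between arms in number or prognosis.

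It would go too far to say that the randomised comparison is bound to be broken, because the document does not show that anyone will leave undosed or will know the arm by then. The size is unknown and may be small. The figures of 1.8 to 6.0 points rest wholly on the assumed 60% retention and the assumed never-dosed shares. With no undosed participants, the planned and all-randomised analyses agree. The change is worth making because it is cheap and removes the dependence on an unstated quantity.

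**What to change.** - **Retention:** make all randomised participants, by assigned arm, the principal set. Start the clock at randomisation and count never-dosed participants as events at day 0.
- **Baseline comparison:** run it on the same all-randomised set.
- **Opioid use:** include all randomised participants in the random regression with their baseline and any follow-up data. Day-0 events do not solve this outcome, since never-dosed participants may have no treatment-period urines, so add a sensitivity analysis that counts those missing urines as positive.
- **At-least-one-dose set:** keep it as a sensitivity analysis.
- **Reporting:** give the number never dosed in each arm, and state when randomisation and disclosure of the arm occur relative to the first dose.

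The cost is a change of analysis wording, with no added participants or assessments. The downside is that a few participants would contribute only baseline data, which may slightly dilute the estimate.

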Subjects: We plan to enroll approximately 200 participants. Veterans who meet the following criteria will be eligible for participation: 1) Males and females between the ages of 18 to 65, current dependence on prescription opioids as evidenced by fulfilling DSM-V criteria for Opioid Use Disorder, signs of opiate withdrawal as evidenced by a COWS score of 7 or greater, self-reported history of opioid dependence, and a positive urine toxicology for opiates; 2) willingness to be detoxified from opioids for buprenorphine maintenance ; 3) for women of childbearing age, a negative pregnancy test at screening with agreement to use adequate contraception to prevent pregnancy, with monthly pregnancy tests obtained during study participation. Exclusion criteria: 1) use of heroin for more than 4 days in the past month; 2) lifetime history of opioid dependence due to heroin alone; 3) ever used heroin intravenously; 4) requirement for current ongoing opioid treatment for adequate pain management; 5) current alcohol, benzodiazepine, barbiturate use with physiologic dependence as determined during screening history and physical, 6) serious unstable medical illness including bradycardia or other arrhythmias, major cardiovascular, renal, endocrine, or hepatic disorders for which buprenorphine treatment is contraindicated or which at the determination of the MD is medically dangerous; 8) serious psychiatric illness including psychosis, bipolar disorder with psychosis; 9) significant current suicidal or homicidal thoughts necessitating a higher level of care; 10) known allergy or intolerance to buprenorphine. Please note that individuals with commonly occurring psychiatric disorders, such as depressive disorders and post traumatic stress disorder, will be included in this “real world” study.

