Medical Management: Medical Management (MM) will be provided for all patients in the study. It is a behavioral intervention designed for patients with alcohol dependence (Pettinati et al. 2000), and similar therapies have been used in other drug abuse trials (Weiss et al. 2011). The objective of MM is to approximate a primary care environment for delivering care for substance dependent patients. In this study MM will be provided by a trained registered nurse and will consist of 12 sessions. The initial visit will be 40-60 minutes and the focus will be on discussing negative consequences of substance use, and educating the patient on medication regimen and compliance. Consecutive sessions will be 15-20 minutes and will be focused on relapse prevention, monitoring of compliance with the medication and psychoeducation. Common elements of the sessions will be identification of high-risk situations and warning signs of relapse. Patients will be encouraged to attend support groups in the community (e.g. Narcotics Anonymous). This intervention was chosen because MM's focus on medical issues is highly compatible with a pharmacologic intervention.

Medication Compliance: In addition to MM we employ a number of strategies to insure maximum compliance with the medication regimen. All medications will be dispensed in clearly labeled prescription vials. During the induction phase all medication will be handled by the nurses on the detox unit. After that all visits and medication dispensing will be done by out nurse ([name]). Before each visit each patient will receive a reminder phone call about his appointment and is also reminded to return the bottle with the study medication regardless of whether any medication is left over. At the beginning of each study visit the left over medication will be counted and the patient will be prompted to report any doubling of dose or missing days of study medication. The session will also provide an opportunity for subjects to review critical

issues and problem areas, the subjects' involvement in any ancillary treatments, and other clinically significant events. Other formal treatment concurrent with their study treatment (including self-help meetings) will be monitored and will be included as a covariate in the analysis.

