 - Center for Epidemiologic Studies Depression (CES-D) scale: CES-D is a 20-item self-report measure of depressive symptoms. The range of scores is from 0 to 60, higher scores reflecting increased depressive symptoms. The CES-D does not heavily depend on pathological items compared with other scales such as Beck Depression Inventory and does not define clinical depression. The CES-D has been shown to be a reliable and valid scale, and it has been used in several epidemiological studies including cocaine users (Bobo et al., 1998; Orme et al., 1986; Weissman et al., 1977). This measure will be obtained at baseline and weekly thereafter.
 - Clinical Opiate Withdrawal Scale (COWS): Withdrawal signs and symptoms will be assessed using a 22-item withdrawal instrument that has been reliably used to assess opiate withdrawal. This scale rates the following items from 0 to 4: lacrimation, nasal congestion, yawning, sneezing, coughing, throat clearing, restlessness, nausea/vomiting, gooseflesh, sweating, stomach cramps, muscle cramps, and feeling hot/cold. This scale will be used on a weekly basis.
 - Columbia-Suicide Severity Rating Scale (C-SSRS): designed to assess suicidal ideation and suicidal intent.
 - Fagerstrom Nicotine Tolerance Questionnaire (FNTQ): This self-report measure assesses the degree of nicotine dependence and has been used widely in smoking studies (Fagerstrom, 1978). This instrument has demonstrated reliability and validity (Pomerleau et al., 1994; Tate and Schmitz, 1993).
 - Post Traumatic Stress Disorder Checklist (PCL-C): to measure PTSD symptoms. The PCL-C is a self-report scale that shares similar reliability with the CAPS. (Weathers et al. 1996)
 - Structured Clinical Interview for DSM-V (SCID) will be used to obtain DSM-V Opiate use dependence, and other Substance Use Disorder diagnoses. The number of dependence syndrome elements endorsed from the DSM-V criteria will assess severity of opiate and other substance use. This instrument will be administered at baseline or in as timely a manner as patient's condition warrants.
 - Time Line Followback: At intake and weekly thereafter, assessments will be made of opioid and other drug use.
 - Weekly cigarette smoking: At intake and weekly thereafter, self-reports will also be made on cigarette smoking.

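### The opioid-use analysis names no baseline opioid-use term, although intake Time Line Followback could sharpen the urine comparison at no extra data cost

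*Combined protocol and SAP*

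**What the plan says.** Section B of Data Analysis Methods plans random regression (HLM) analyses that "will be conducted to examine if the change in opioid use behavior over time varies as a function of the treatment factors". It does not say whether opioid use means weekly urines or Time Line Followback, whether the intake value enters the model, or whether the tested contrast is a slope or a mean level. Baseline characteristics appear there only in a between-arm comparison meant to check the randomisation, with no stated consequence.

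Section A sizes the trial differently. It plans that "we will recruit a total of 200 subjects, 100 subjects in each treatment arm" and gives an effect size "for the number of opioid positive urines during the treatment period", which is a total or mean-level contrast.

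Three other places bear on the point:
- Time Line Followback (Psychosocial Assessments, and the baseline list under Assessments): "At intake and weekly thereafter, assessments will be made of opioid and other drug use".
- Subjects: entry requires "a positive urine toxicology for opiates".
- Medication Compliance: concurrent formal treatment "will be monitored and will be included as a covariate in the analysis". This is the only covariate named anywhere, and it arises after randomisation.

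**The concern.** Amount of opioid use before treatment is a natural candidate to predict use during treatment. The trial records it but gives it no stated role in the comparison of doses. Adjusting for a prognostic baseline measure narrows the interval for the dose effect and removes the part of any chance imbalance that the measure explains. Baseline urine is a poor substitute: with a positive result required at entry it is close to constant. It may not be strictly constant, since Protection of subjects lets the study physician randomise someone in withdrawal before laboratory results are back.

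Discretion is also at stake. A plan that tests baseline differences, names no baseline covariate and does not say what follows from the tests leaves room to pick covariates after imbalances have been seen.

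**Working it through.** **Inputs from the documents.** 200 participants, 100 per arm; outcome for sizing, the number of opioid-positive urines; weekly urines over 12 weeks.

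**Inputs assumed.** Two-sided alpha 0.05 and 80% power (neither is stated); baseline-outcome correlation r from 0.1 to 0.5 (not stated); outcome treated as continuous; no dropout.

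**The plan's own figure.** Section A states: "Our sample of 200 will require an effect size of .25". Alpha, sidedness, power and the effect-size metric are missing, so the figure cannot be reproduced. Read as Cohen's d = 0.25, 100 per arm gives about 42% power. Read as Cohen's f = 0.25 (d = 0.50), it gives about 94%. The calculation below therefore starts from the detectable difference.

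**Mean-level contrast.** For a two-sample t-test with 100 per arm, the d detectable with 80% power is 0.398. Adjustment for a baseline measure with correlation r multiplies the residual variance by 1 − r² and the standard error by √(1 − r²). So the detectable d is 0.398 × √(1 − r²), and the equivalent unadjusted sample size is 200 / (1 − r²).

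| r | √(1 − r²) | Fall in standard error | Detectable d | Equivalent N | Power at d = 0.40 |
|---|---|---|---|---|---|
| 0 | 1.000 | 0% | 0.398 | 200 | 80% |
| 0.1 | 0.995 | 0.5% | 0.396 | 202 | 81% |
| 0.2 | 0.980 | 2.0% | 0.390 | 208 | 82% |
| 0.3 | 0.954 | 4.6% | 0.380 | 220 | 84% |
| 0.5 | 0.866 | 13.4% | 0.345 | 267 | 90% |

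**Treatment-by-time slope.** This is the contrast suggested by the wording of section B, and the table does not carry over to it. I computed the generalised least squares standard error of the slope difference for weeks 1 to 12, with 100 per arm and residual variance 0.5. The random-intercept variance was 0.5 and the random-slope variance 0 or 0.003. All of these are illustrative values, and the baseline is taken as the same measure as the outcome.

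| Setting | No baseline | Baseline main effect | Main effect plus baseline × time | Baseline as time-0 outcome |
|---|---|---|---|---|
| Random intercept only | 0.00836 | 0.00836 | 0.00836 | 0.00741 |
| Random slope, uncorrelated with intercept | 0.01140 | 0.01140 | 0.01140 | 0.01072 |
| Random slope, correlation ±0.4 with intercept | 0.01140 | 0.01140 | 0.01119 | 0.01072 |

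A main effect alone does not change the slope's precision. Adding the interaction with time helps only where baseline predicts the slope, here by about 2% (1 − 0.01119/0.01140). Using the intake value as the time-0 outcome helps more, by 6% to 11% (1 − 0.01072/0.01140 and 1 − 0.00741/0.00836). That route is open only when outcome and intake value come from the same instrument.

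**The case against.** A reader might infer that the model holds only treatment and time, that baseline is shut out, and that precision is thrown away for nothing. The documents do not support this. The plan gives one sentence and no complete covariate list, and Medication Compliance promises at least one further covariate. The plan is silent on baseline; it does not exclude it. Because Time Line Followback is taken at intake and weekly, a model of change could well carry the intake value as time 0, and then that information is used. This part of the objection stands for Time Line Followback outcomes. It does not reach weekly urines, for which a self-report measure cannot be the time-0 value and the baseline urine barely varies.

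A reader might also apply the gains in detectable d to the change-over-time contrast. The second table shows that a baseline main effect brings nothing there.

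Three further points stand:
- The correlation is unknown. Entry criteria that select active, dependent users may compress baseline use and weaken it; at r = 0.1 to 0.2 the gain is trivial.
- The documents give no look-back window or derived variable, so opioid-use days must be defined before they can serve as a covariate.
- For binary weekly urines in a logistic mixed model, 1 − r² is only a guide, and adjustment also changes the conditional effect being estimated.

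**Conclusion.** The point holds as a limited one about efficiency. The analysis section names no baseline opioid-use term, and for the urine outcome on which the trial is sized, intake Time Line Followback is the practical source of baseline information on amount of opioid use. On that mean-level contrast the gain runs from negligible (0.5% to 2% in standard error at r = 0.1 to 0.2) through 5% at 0.3 to 13% at 0.5. The detectable d moves from 0.398 to between 0.396 and 0.345. These sizes rest on assumed correlations, two-sided alpha 0.05, 80% power, complete data and a continuous-outcome approximation.

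The omission of a baseline term does not by itself bias the result: randomisation keeps the unadjusted contrast unbiased. The omission is certain; the size of the benefit is not. Pre-specification is still worthwhile, because one covariate costs almost nothing with 200 participants and it closes the choice of covariates after the baseline tests.

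**What to change.** In section B of Data Analysis Methods:

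- Name the tested contrast for each opioid-use outcome (mean level over treatment, or treatment-by-time slope).
- State that the weekly-urine models include pre-randomisation Time Line Followback opioid-use days as a pre-specified fixed covariate, and define the look-back window. If the slope is tested, add the covariate's interaction with time.
- State that Time Line Followback models use the intake value either as the time-0 outcome or as a covariate, not both.
- State that covariates are not selected from the baseline comparison tests.
- If urines are analysed by logistic mixed regression, state that the effect is conditional on baseline, or report a marginal effect.

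The cost is a few sentences and one variable definition. No new data are collected, provided the intake assessment is completed before randomisation.
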